Treg inhibition/recruitment (Treg MLR) and regulation of cytotoxic T cells (micro-cell mediated lympholysis, m-CML) induced by IS therapies and in clinical tolerance trials (14, 17-20). Also, we have utilized peripheral blood/allograft immunophenotyping for regulatory cell populations and immunoregulatory proteogenomic assays to look for signatures of tolerance and CKD in LT recipients (13, 21). Yet the presence of Treg populations and differential gene array snapshots in 'already-withdrawn' patients or patients currently on IS therapy, without a clear understanding of their utility in monitoring during withdrawal, only provides circumstantial evidence for their role in tolerance. An array of assays performed throughout the tapering and withdrawal period, as described herein, would provide a more accurate measure of the effects of SRL on Treg function and immunoregulatory gene/protein expression, supporting their use as predictors of tolerance in future protocols.

With the above background and rationale, we expect to develop two strategies to promote the ability to achieve and monitor LT tolerance. The first is initial CNI to SRL conversion to promote systemic immunoregulation (already performed in our preliminary work (13)), followed by SRL minimization and withdrawal (this Institutional Review Board [IRB] submission). This is to be compared to the established literature success rate ($\approx 20\%$) of CNI withdrawal, as we do not feel it is clinically acceptable to include this as a control group (6). *We hypothesize that the clinical use of SRL promotes immunoregulatory pathways and provides higher IS withdrawal success compared to CNI therapy.* The second strategy aims to identify immunologic and proteogenomic assessments of immunoregulation, potentially enhanced by SRL conversion and predicting/correlating with successful IS withdrawal.

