1.2 Preclinical Data

Preliminary Data: We demonstrated that liver transplant (LT) recipients on SRL monotherapy had higher percentages of peripheral blood mononuclear cell (PBMC) immunophenotypic Tregs (CD4+CD25Hi+Foxp3+ cells) compared to recipients on CNIs (12). This led to a recently published CNI to SRL conversion trial demonstrating increased percentages of PBMC/bone marrow Tregs and PBMC DCregs (ILT3/4+) in LT recipients converted from tacrolimus to SRL monotherapy (13). Liver biopsy immunohistochemistry FOXP3:CD3 and CD4:CD8 ratios were significantly higher after conversion. Patient sera on TAC but not SRL suppressed Treg generation in mixed lymphocyte reactions. Finally, consistent with prior reports of genomic expression patterns and cellular assays as signatures of tolerance (16), we detected the expression of 289 novel genes and 22 proteins, several important in immunoregulatory pathways, after SRL conversion. In a separate in vitro study, we also demonstrated robust allospecific regulatory effects of SRL in Treg mixed lymphocyte reactions (14). Our preliminary data, in conjunction with other clinical and laboratory reports, provide the mechanistic rationale for the

concept that SRL may facilitate IS withdrawal in LT and that such assays should be tested in parallel as biomarkers of tolerance. We hypothesize that SRL will promote regulatory gene/protein expression patterns in the peripheral blood AND in the allograft, which can then be utilized as predictive assays in tolerance trials. To robustly test this hypothesis, we will collect serial blood and allograft samples before/after withdrawal and at the time of biopsy for possible rejection, all to be tested as markers of immunoregulation. This will consist of assays similar to those performed in our recent work (12, 13, 21).

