Primary Objective: The goal is to determine if operational tolerance (normal graft function without IS therapy x 12 months) can be achieved successfully in LT recipients withdrawn from SRL.

Secondary Objectives

1. To investigate if cellular, allograft and proteogenomic metrics of immune regulation are predictive of and persist following successful SRL withdrawal in LT recipients.
2. To analyze any initial clinical benefit of minimization and withdrawal of SRL therapy.

3 Study Design

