After long term (> 3 years post-LT, > 3 months on SRL monotherapy) on SRL monotherapy, inclusion/exclusion criteria will be reviewed and if appropriate, consent as above will be obtained. If the patient agrees and signs consent, baseline standard of care screening laboratories complete blood count, comprehensive metabolic panel, sirolimus (CBC, CMP, SRL trough level, fasting lipid profile, hemoglobin A1C [HbA1C], urine protein/creatinine ratio) and non-standard of care biomarker assays (blood immunophenotyping, proteogenomics) and liver biopsy (histology and graft immunohistochemistry) will be performed as dictated by the protocol. In addition, the liver biopsy will be used to determine stability in graft function (i.e. no evidence of rejection or immune-mediated hepatitis) before considering minimization/withdrawal. SRL minimization/withdrawal will only be performed if clinically, biochemically and histologically [by biopsy; liver transplant pathology read ([name], [name])] stable. Throughout the entire study, liver function tests will be monitored every 2 weeks (monthly is standard of care, so the interim non-standard of care 2 week blood tests will be covered by the study funds). Patients entering the minimization/withdrawal phases will be reduced by a total dose of 50% of their baseline dose every month until patients are on 0.5 mg SRL daily. At this point, every other day dosing will begin x 1 month. If no LFT abnormalities, twice weekly dosing x 1 month, then once a week dosing x 1 month. Prior to complete discontinuation, repeat clinical (screening labs above) and blood biomarker assays (blood immunophenotyping, proteogenomics) will be performed. Liver biopsy will not be performed at this juncture unless there are biochemical signs of liver injury. If complete withdrawal is deemed safe (no evidence of biochemical abnormalities) patients will be withdrawn completely (i.e. the once/week SRL dose discontinued) and followed off IS therapy for one year. In this time period, liver function tests will be monitored every 2 weeks, as usual, and repeat clinical (screening labs above), liver biopsy and blood (blood immunophenotyping, proteogenomics) assays performed at the end of this year or at any concern for rejection.

Blood and Tissue Samples

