Standard of care laboratories (CBC, CMP) will be performed every month on all patients, and only LFTs performed in the interim 2 weeks between each month (non-standard of care; covered by the study funds) until complete withdrawal. 3 green top 5 mL and 3 red top 5 mL tubes of blood for biomarker assays will be taken on all patients prior to study enrollment, prior to complete withdrawal, and one year after withdrawal or at the time of suspected rejection. Liver biopsy (one 3 cm biopsy- 2 cm for histology and 1 cm for genomic assays) will be performed at baseline (pre-minimization) and 1 year post withdrawal. A separate clinical informed consent will be obtained each time a liver biopsy is performed. If the patient develops elevation in liver transaminases requiring a liver biopsy at any stage of the study protocol, blood (all for immune monitoring (IM) assays) will be requested from the patient at the time of the biopsy. If rejection occurs, the patient will be followed in the study until completion but not be further withdrawn from SRL or have a liver biopsy at the end of the study

Follow-up

Laboratory follow-up is described above- every 2 weeks throughout the trial until complete withdrawal. Any biochemical (or clinical) signs or significant liver function test abnormalities will be acted on immediately either by liver biopsy or a pause in IS withdrawal per investigator discretion. All patients will be seen in the clinic every 3 months to assess for any new signs or symptoms or resolution of drug side effects in the minimization or withdrawal arm. Quality of life questionnaires; Post Liver Transplant

Quality of Life Instrument (pLTQ) and the Promis-29 profile v1.0 will be administered at the study onset and after successful vs. unsuccessful withdrawal (end of study)

Outcome Measures

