The primary outcome will be the proportion of patients off SRL therapy with normal liver biochemistry and graft histology at 12 months (i.e. tolerant). Thus, the incidence of graft dysfunction (acute rejection, immune mediated or autoimmune hepatitis, chronic rejection) or non-tolerance will be assessed in this SRL withdrawal group and compared to the historical CNI group (20% tolerant; 80% failure) as the primary endpoint. This rate will be a composite of the cumulative number of biopsy-proven graft dysfunctions requiring conversion back to SRL or additional IS therapy or discontinuation of minimization/withdrawal that occur during the course of the study. Major secondary measures compared will be the predictive capacity of the blood and graft biomarker assays (immunophenotyping, genomic/proteomics) before and after minimization/withdrawal in the success vs. failure groups. Clinical secondary outcomes will be compared: the number of infectious complications, liver biopsy complications, cardiovascular outcomes (i.e. blood pressure, diabetes control, lipid levels), renal function, hematopoietic parameters, gastrointestinal effects, or other side effects of SRL that may or may not improve or develop with minimization/withdrawal. These will all be documented by a study database during patient visits, electronic charts and/or by phone communication. Finally, quality of life (Post Liver Transplant Quality of Life Instrument (pLTQ) and the Promis-29 profile v1.0) will be analyzed at the end of the study to determine the effect of IS minimization/withdrawal on other health benefits.

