any patient throughout the study developing liver dysfunction (direct bilirubin >1 mg/dL; ALT, AST, or AlkPhos > 2xULN), this will be confirmed on a repeat blood test within 1-2 weeks and if persistent, liver biopsy will be performed. Immediately before complete withdrawal, i.e. repeat clinical (screening labs) and blood assays will be performed. If complete withdrawal is deemed safe (no evidence of biochemical abnormalities, i.e. direct bilirubin < 1 mg/dL; ALT, AST, or AlkPhos < 2xULN), patients will be withdrawn completely (i.e. the once/week SRL dose discontinued) and followed off SRL therapy for one year. In this time period, liver function tests will be monitored every 2 weeks. At 12 months following withdrawal, the same history and physical, QOL survey, screening labs and blood IM assays will be performed as in the study initiation, as well as the liver biopsy- all for the primary endpoint. If rejection or immune-mediated hepatitis is seen on this post-withdrawal biopsy or at any time during the study period, the patient will be reinitiated on IS therapy appropriately per the PI and not have another withdrawal attempt. All patients will be followed until 1 year post-attempted withdrawal, even if unsuccessful, although patients developing rejection or resumption of IS prior to this period will not have a final liver biopsy performed (i.e. only those presumed tolerant or who did not have rejection).

Blood and Tissue Samples

Standard of care laboratories complete blood count, liver function tests (CBC, LFTs) will be performed every 2 weeks on all patients. Please see Figure 1 above for sample collections. A separate clinical informed consent will be obtained each time a liver biopsy is performed. If the patient develops elevation in liver transaminases requiring a liver biopsy at any stage of the minimization/withdrawal phase, blood assays will be requested from the patient at the time of the biopsy. These immunological data in rejecting patients will be important to compare to patients who successfully are minimized and withdrawn.

Follow-up

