6.6 **Visit 5: Post-Withdrawal (18 month clinic visit- study end):** At 12 months following withdrawal, the same history and physical, the Post Liver Transplantation Quality of Life and Promis-29 quality of life surveys, labs (CBC, CMP, HBs1C, Lipid profile, Urine prot/cr ratio- SOC; and tolerance/immunophenotyping/genomic/proteomic assays- research) will be performed as in the study initiation, as well as the research liver biopsy- all for the primary endpoint. If rejection or immune-mediated hepatitis is seen on this post-withdrawal biopsy or at any time during the study period, the patient will be reinitiated on IS therapy appropriately per the PI and not have another withdrawal attempt. All patients will be followed until 1 year post-attempted withdrawal, even if unsuccessful, although patients developing rejection or resumption of IS prior to this period will not have a final liver biopsy performed (i.e. only those presumed tolerant or who did not have rejection).

7 Statistical Plan

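### The plan does not say which biomarker samples count as prediction, and it states no optimism correction for signature accuracy

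*Combined protocol and SAP*

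**What the plan says.** Secondary objective 1 (section 2) asks whether immune metrics "are predictive of and persist following successful SRL withdrawal in LT recipients". Section 3.1 (Outcome Measures) turns this into the "predictive capacity of the blood and graft biomarker assays (immunophenotyping, genomic/proteomics) before and after minimization/withdrawal in the success vs. failure groups".

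Section 3.1 (Blood and Tissue Samples) schedules biomarker blood "prior to study enrollment, prior to complete withdrawal, and one year after withdrawal or at the time of suspected rejection". Biopsies are planned at baseline and one year after withdrawal. At the pre-withdrawal point, "Liver biopsy will not be performed at this juncture unless there are biochemical signs of liver injury". Section 1.2 describes serial blood and allograft samples "before/after withdrawal and at the time of biopsy for possible rejection, all to be tested as markers of immunoregulation". Section 4.3 says of samples taken at a for-cause biopsy: "These immunological data in rejecting patients will be important to compare to patients who successfully are minimized and withdrawn".

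The study summary words objective 2 as correlation with successful withdrawal, and 1.1 speaks of predicting or correlating. Section 1.1 also presents serial assays as better than single snapshots, "supporting their use as predictors of tolerance in future protocols".

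Section 7.2 describes, mostly in the past tense, t-tests with a nonparametric analogue, fold change, AUROC, q-values, accuracy, sensitivity and specificity. It names no cross-validation, bootstrap or hold-out set. Section 7.1 says the results will guide power calculations for larger studies of the predictors found, and that patients can act as their own controls for rejection versus success.

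**The concern.** A predictor has to be measured before the outcome it predicts. If the last available sample enters a success-versus-failure comparison, a marker that changes only once rejection is under way can be reported as predictive. The risk is greatest for graft assays: histology helps define the outcome, and baseline is the only planned biopsy before it.

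Separately, accuracy computed in the patients used to choose a signature is biased upward, and with 25 or fewer patients the bias can be large. q-values address multiple testing; they do not correct the accuracy estimate.

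At stake are secondary objective 1 and the inputs to the later power calculations.

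**Working it through.** **Inputs from the documents.** Up to 25 patients (3.1). Failure hypothesized at 50% (1.4): 25 × 0.5 = 12.5, taken as 12 failures and 13 successes. Historical success of 20% (3.1): 25 × 0.2 = 5 successes and 20 failures. Significance at P<0.05 (7.2), taken as two-sided. The documents give no biomarker effect size, power or target AUC, so there is no planned figure to reproduce.

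**Sample times set against outcome.**
- Baseline blood and biopsy: before the event in everyone who starts minimization.
- Pre-withdrawal blood: before the event, but only in those who reach that point. Patients who reject during the taper do not.
- Last sample: one year in successes; suspected rejection in failures detected earlier. Sections 4.3 and 6.6 add a third case, "If rejection or immune-mediated hepatitis is seen on this post-withdrawal biopsy or at any time during the study period": there the timing matches the successes, but the sample is still taken during rejection.
- The split is not perfectly clean. A patient whose for-cause biopsy is negative also gives blood then and can still succeed.

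**Timing effect (assumed inputs).** Take a marker with no baseline difference that shifts by d SD at rejection in a share p of failures. Then AUC = p·Φ(d/√2) + (1−p)·0.5.

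| p | d = 0.5 | d = 1 | d = 1.5 | d = 2 |
|---|---|---|---|---|
| 1 | 0.64 | 0.76 | 0.86 | 0.92 |
| 0.75 | 0.60 | 0.70 | 0.77 | 0.82 |
| 0.5 | 0.57 | 0.63 | 0.68 | 0.71 |

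The baseline AUC is 0.50 throughout. At 12 v 13 and d = 1, a t-test on the last sample is significant in 67% of simulated data sets if all failures shift, 40% if 9 of 12 do and about 20% if 6 of 12 do, against 5% at baseline.

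**Optimism (assumed in-sample selection and scoring).** Null markers, 12 v 13, best markers chosen by t-statistic and summed into a score:

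| Signature | correlation 0 | 0.6 | 0.8 |
|---|---|---|---|
| best 1 of 10 | 0.71 | 0.69 | 0.66 |
| best 3 of 20 | 0.83 | 0.74 | 0.69 |

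These are mean apparent AUROCs. With selection repeated inside 5-fold cross-validation the mean is about 0.5. The candidate count is not stated. If it matched the earlier study's 289 genes + 22 proteins = 311, with independent noise and 5 features chosen, the apparent AUROC would be 0.975. The size therefore depends heavily on the assumptions; the direction does not.

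**Carry-forward (assumed).** A later study sized on a 1 SD difference needs n = 2(1.96 + 0.84)²/1² = 15.7, or 16 per group by normal approximation. The exact t-test gives 78% power at 16, so 17 are needed. If the true pre-event difference were 0.5 SD, power at 17 per group would be about 29%.

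**Precision.** The Hanley-McNeil 95% half-width around an AUROC of 0.75 is 0.20 at 12 v 13, and 0.22 to 0.27 at 5 v 20 depending on which group is labelled positive. In the widest case the upper limit is 0.75 + 0.27 = 1.02, above 1, so a symmetric interval does not suit these numbers.

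**Own control.** Each patient has one outcome, so rejection versus success is a contrast between different patients. The paired tests in 7.2 apply to change within a patient.

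**The case against.** The plan can be read more kindly. Correlation is an explicit aim in the study summary and in 1.1, and rejection-time samples are proper for that aim. Section 4.3 compares rejecting with successful patients without calling those data predictive, and 1.2 calls the samples markers of immunoregulation. The wording of secondary objective 1 hints at early samples for prediction and later ones for persistence. All of this stands. A reader might infer that the plan intends to use rejection-time samples as predictors; the documents do not say so. They leave the choice open.

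A reader might also infer that signatures will be scored in the patients used to select them. Section 7.2 recounts earlier studies, and whether those used resampling cannot be seen. Only the absence of a stated correction is established. q-values are named, and a strict q<0.05 entry rule would prevent most noise signatures (about 4 to 6% of null data sets contain any such marker), but no entry rule is given.

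Finally, 1.1 calls the signatures preliminary and subject to validation, and 7.1 foresees prospective testing. That limits the harm. It does not remove it, because a later study could be sized on the inflated values before validation exposes them.

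**Conclusion.** The concern holds as an omission. Predictive claims have no assigned sample time, and signature accuracy has no stated optimism correction. Every bias size above rests on assumed shifts, marker counts, correlations and signature sizes, so the figures show direction and plausible scale, not this trial's bias. It would go too far to say that later studies will be too small: they could be, if designed on rejection-time or uncorrected values. The 12 v 13 split is itself a best case, since enrollment is up to 25 and the baseline biopsy can stop entry. The primary endpoint is unaffected. For an exploratory aim in a single-center pilot, this is a change the sponsor should make, at the lighter end of that category.

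**What to change.** (a) In 3.1 and 7.2, base predictive claims on baseline blood and biopsy in all who start minimization. Use the pre-withdrawal blood sample as a landmark analysis among those who reach it, stating how many failed earlier. Report one-year samples under persistence, and rejection-time samples, including rejection first found at one year, as correlates.

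(b) In 7.2, report signature AUROC, sensitivity and specificity with cross-validation or bootstrap, repeating marker selection in each resample, and with confidence intervals suited to small samples.

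(c) In 7.1, drop the own-control statement for rejection versus success and keep it for within-patient change.

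The cost is wording and analysis code, with no new samples or visits. The price is lower reported accuracy, wide intervals and a smaller landmark set. With 80% power, two-sided 0.05 and an unpaired t-test, the detectable difference is 1.17 SD at 12 v 13. It rises to 1.28 SD with 13 successes and 9 failures, or 1.47 SD with 13 and 6, if 3 or 6 of the 12 failures (assumed) occur before the landmark.

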3.2 Primary Study Endpoints

The primary outcome will be the proportion of tolerant patients off SRL therapy with normal liver biochemistry and graft histology at 12 months.

3.3 Secondary Study Endpoints

Secondary outcomes will include the incidence, severity and reversibility of rejection, patient/graft survival, resolution of SRL and other non-specific IS effects, and the assessment of clinical/immunological biomarkers of tolerance.

3.4 Primary Safety Endpoints

Safety of the study will be monitored closely and determined by the the incidence, timing, severity and reversibility of rejection with withdrawal, graft function (biochemical and histological) throughout and at the end of the study, resumption of other IS therapies due to rejection and their toxicities (SRL,CNIs, prednisone, mycophenolic acid, other), complications from phlebotomies and liver biopsies, and patient/graft survival (patient/graft loss very unlikely to occur based on prior studies)

4 Subject Selection and Withdrawal

4.1 Inclusion Criteria

- 1) Adult male and female recipients of all races, ≥ 18 -75 years of age
- 2) Patients who underwent primary living or deceased donor liver transplantation ≥ 3 years (previous to screening) and on ≥ 3 months of stable SRL monotherapy
- 3) Recipient of single organ transplant only
- 4) Liver transplant for non-immune, non-viral (no hepatitis B or hepatitis C virus unless currently non-viremic) causes
- 5) Ability to provide informed consent and to comply with the study protocol of IS withdrawal.

4.2 Exclusion Criteria

- 1) Inability or unwillingness to provide informed consent
- 2) Acute cellular rejection within 12 months prior to enrollment
- 3) Viral (viremic hepatitis B virus [HBV] or hepatitis C virus [HCV]) or immune-mediated liver disease (Autoimmune hepatitis, primary sclerosing cholangitis, primary biliary cirrhosis) history
- 4) Abnormal liver function tests: Direct bilirubin ≥ 1 mg/dL; ([ALT, AST, GGT] or alkaline phosphatase [AlkPhos] $\geq 2x$ [ULN]); 5) Abnormal graft histology at enrollment: a) \geq Grade 2 inflammation or stage 2 fibrosis; b) Acute or Chronic Rejection; c) De-novo Autoimmune Hepatitis; d) inflammation of $>50\%$ of portal tracts; e) Other pathology not-specified but deemed high risk per the PI and pathologist; 6) Ongoing or recurrent substance abuse
- 7) Retransplantation or combined liver-other organ
- 8) Human Immunodeficiency Virus(HIV) co-infection
- 9) Glomerular Filtration Rate (GFR) <30 ml/min by estimated glomerular filtration rate ([eGFR]-[MDRD-4])

